The effect of fractionation is complicated for SBRT, and fractionation regimens vary from center to center. A number of fractionation schedules are undergoing evaluation [155]. In the U.S., a frequently used schedule for peripheral lung tumors is 60 Gy in 3 fractions with a total BED of 180 Gy. In Europe, Japan, and China, however, a BED >100 Gy is more commonly delivered in 4-10 fractions. Particularly in China, regimens with fraction size less than 12 Gy have been preferred. Selection of fractionation should maximize the therapeutic ratio of tumor control versus normal tissue toxicity by taking the tumor size and location into consideration for an optimized therapeutic gain [156] [157]. Overall, for tumors less than 3 cm, there is no significant difference in tumor control rates between various fractionation regimens as long as more than 100 Gy BED is given [150, 158]. For tumors larger than 3 cm, higher doses (BED of 120 Gy or above) may be needed. Similar to RODS, distant failure is the main cause of death [159]. Fractionation regimens with tumor BED around 120 Gy in 3-5 fractions include 16 Gy x 3, 13 Gy x 4, and 11 Gy x 5. The available data are compelling enough for SBRT to be considered an established treatment option in patients who are medically inoperable or for those patients who have refused surgical resection [132, 150, 160].

1.2.2

Toxicity of SBRT

Toxicity following SBRT has been limited. Reported long-term toxicity exceeding grade 2 Common Toxicity Criteria (CTC v. 3.0) is seen in less than 10% of patients and was mainly observed in patients with large or centrally located tumors [121, 135, 161, 162] when doses to the proximal bronchial tree were not strictly limited. In the series by Onishi [129], pulmonary complications exceeding grade 2 were observed in 14 patients (5.4%). Timmerman, et al. reported the need for caution when a BED of 180–210 Gy was administered for centrally located tumors adjacent to the mediastinum [134]. In the patients treated by Lagerwaard, et al., using a 'risk-adapted' approach with the BED limited to 105 Gy for central tumors, early toxicity was mild with fatigue (32%), nausea (10%), and chest pain (8%) as the most frequently encountered acute side effects [135]. Late toxicity was uncommon with radiation pneumonitis exceeding grade 2 in 6 patients (3%). Rib fractures and chronic pain syndromes located at the chest wall were observed in 4 and 3 patients, respectively.

1.2.3

Quality of Life After SBRT

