11.2.1.2 PET Tumor Response

Guidelines for assessing post-SBRT changes on PET/CT will be per the table below, defined by Kong, et al. at the University of Michigan [257], using the blood pool in the aortic arch as a reference. This system is considered to be more reproducible than that of PERECIST [258] which uses the liver as a reference. The aortic arch is also less likely to be confounded by disease conditions in the liver which may increase FDG-activity. Metabolic tumor volumes will also be assessed and recorded.

PET Tumor Response of Irradiated Target Lesions

Complete Metabolic Response (CMR)	Tumor FDG-activity decreased to less than mean background of the aortic arch blood pool.
Partial Metabolic Response (PMR)	At least a 30% decrease in the maximum of relative tumor FDG-activity of target lesions
Progressive Metabolic Disease (PMD)	At least a 20% increase in the maximum of relative tumor FDG-activity of target lesions
Stable Metabolic Disease (SMD)	Neither sufficient reduction to qualify for MPR nor sufficient increase to qualify for MPD

The percentage of decrease or increase was globally estimated based on readings of (tumor activity-aorta activity)/aorta activity.

11.2.2 Local regional tumor control is defined as freedom from local-regional recurrence after RODS and freedom from progression of local primary tumor and disease occurrence at nodal regions after SBRT.

Local-regional recurrence after RODS includes recurrence, defined by CT, confirmed by PET/CT whenever possible, i.e., development of tumor masses at the site of resection, or hilum (N1 nodal region), mediastinum (N2-N3 nodes), or ipsilateral supraclavicular fossa for upper lobe tumors (N3 nodes), or within 3 cm of the staple line of RODS.

Local regional progression after SBRT includes tumor progression on CT per RECIST criteria, confirmed by PET/CT, within the same lobe, hilum (N1 nodes), mediastinum (N2-N3 nodes), or ipsilateral supraclavicular fossa for upper lobe tumors (N3 nodes), or within 3 cm of original PTV.

Local progression is defined as at least a 20% increase in the sum of diameters of the target lesions, taking as reference the smallest sum on study (this includes the baseline sum if that is the smallest on study). In addition to the relative increase of 20%, the sum must also demonstrate an absolute increase of at least 5 mm. (Note: the appearance of one or more new lesions is also considered progression).

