13.0 STATISTICAL CONSIDERATIONS

13.1 Primary Endpoint

13.1.1 Two-year local-regional tumor control, which is defined as freedom from local-regional recurrence after RODS and freedom from progression of local primary tumor and disease occurrence at nodal regions after SBRT (see Section 11.2.2)

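### The primary-endpoint definition is inconsistent about which sites count as failure after SBRT, and its closing paragraph carries a new-lesion rule with no site limit

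*Combined protocol and SAP*

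**What the plan says.** Section 13.1.1 sets the primary endpoint as two-year local-regional control. For the SBRT arm this means "freedom from progression of local primary tumor and disease occurrence at nodal regions after SBRT", and the reader is sent to section 11.2.2, which opens with the same definition.

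Section 11.2.2 then has three further paragraphs.

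- **RODS.** Recurrence is tied to a list of sites. It begins with "development of tumor masses at the site of resection" and continues with hilum, mediastinum, ipsilateral supraclavicular fossa for upper lobe tumors, and a 3 cm zone around the staple line. There is no new-lesion clause.
- **SBRT.** Local-regional progression is RECIST progression on CT, confirmed by PET/CT, at listed sites: same lobe, hilum, mediastinum, ipsilateral supraclavicular fossa for upper lobe tumors, "or within 3 cm of original PTV".
- **Local progression.** The closing paragraph reads: "Local progression is defined as at least a 20% increase in the sum of diameters of the target lesions". It adds the 5 mm absolute increase and the parenthetical note "Note: the appearance of one or more new lesions is also considered progression". It names neither a site nor an arm.

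Section 11.2.3 classifies failures as local, regional nodal or distant for both modalities. Section 13.2.4 lists distant metastases separately from local-regional failure.

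**The concern.** The closing paragraph repeats the general RECIST progression rule of section 11.2.1.1. That rule covers the whole body, and here it sits under the word local without a restriction. Its size criterion needs target lesions and a smallest sum on study, which exist after SBRT but not after resection. In practice the paragraph therefore speaks to one arm.

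An assessor who applied it literally would score a new brain, bone or contralateral lung lesion, with a stable treated nodule, as local progression after SBRT. The same lesion after RODS would not be a local-regional failure. Section 1.2.1 says that, as after RODS, "distant failure is the main cause of death", so such lesions are not a remote possibility. The comparison is one of non-inferiority, and an error of this kind would count against SBRT for reasons unrelated to local-regional control.

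A second inconsistency does not involve distant disease. A new nodule in the same lobe but more than 3 cm from the PTV is a failure under the SBRT paragraph, yet the opening definition and 13.1.1 do not name that site.

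**Working it through.** **Step 1. The definitions side by side.** The question is whether each new finding after SBRT, with the treated nodule stable, is a local-regional failure.

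| New finding after SBRT | 13.1.1 and 11.2.2 opening | 11.2.2 SBRT paragraph | 11.2.2 closing paragraph, literal | 11.2.3 |
|---|---|---|---|---|
| Same lobe, more than 3 cm from PTV | not named | yes | yes | local |
| Another ipsilateral lobe, 2-3 cm from PTV | not named | yes | yes | distant |
| Contralateral supraclavicular node | nodal regions not specified | no | yes | regional |
| Brain, bone or contralateral lung | no | no | yes | distant |

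No two columns agree on every row. For the last row, the RODS paragraph gives no.

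**Step 2. The plan's own sample size.** Inputs from section 13.3: control 0.90 with RODS and 0.75 with SBRT, error probability 0.20, power 0.80. Sidedness is not stated. With a one-sided 0.20 level, pooled variance and no continuity correction:

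n = [z√(2p̄(1−p̄)) + z√(0.90×0.10 + 0.75×0.25)]² / 0.15², with z = 0.8416 and p̄ = 0.825.

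This gives 35.65, so 36 per arm and 72 in total. Then 72 × 1.05 = 75.6, so 76. The plan's figure reproduces, and the endpoint wording does not enter it.

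**Step 3. Worst-case size of the literal reading.** Assumptions:

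- True local-regional control is 90% in both arms, with 36 patients per arm.
- The margin is 15 points, tested by a one-sided unpooled Wald non-inferiority test at 0.20. Section 13.5.1 specifies only a test of binomial proportions, so the form of the test is assumed.
- A fraction d of locally controlled SBRT patients has a distant new lesion by two years. All of these are scored as local failures, and none is in the RODS arm. The documents give no two-year distant-only rate, so 5%, 10% and 15% are illustrative.

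Measured SBRT control = 0.90 × (1 − d). The chance of declaring non-inferiority is the sum of the two binomial probabilities over every outcome pair whose lower confidence limit for SBRT minus RODS lies above −0.15.

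| d | Measured SBRT control | Chance of declaring non-inferiority |
|---|---|---|
| 0 | 0.900 | 0.91 |
| 5% | 0.855 | 0.72 |
| 10% | 0.810 | 0.47 |
| 15% | 0.765 | 0.26 |

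The level matters. At one-sided 0.10, which the documents do not state, the four figures are 0.79, 0.53, 0.29 and 0.14.

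**Step 4. Per patient.** One misclassified SBRT patient moves the observed rate by 1/36 = 2.8 points. The 15-point margin equals 0.15 × 36 = 5.4 patients.

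**The case against.** The strongest reply is that the passages should be read together. The endpoint is local-regional control, and the SBRT paragraph directly above the closing one is limited to listed sites. That paragraph invokes RECIST, and the closing paragraph most naturally supplies the RECIST threshold. Calling a brain metastasis local contradicts the term being defined. Section 11.2.3 puts contralateral lung and other distant sites under distant failure for both modalities, and 13.2.4 keeps distant metastases apart. The opening sentence can also be taken as a summary of the site lists below it, and 11.2.3 agrees that same-lobe disease is local. Finally, the closing paragraph names no arm, and its new-lesion note is not restricted to SBRT.

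Most of this stands. A reader might infer that the plan counts distant metastases as local failure after SBRT, or that it is built to disadvantage that arm. The documents do not support either inference: their evident intent is to exclude distant disease in both arms.

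The reply does not remove the inconsistency. Section 13.1.1 cites 11.2.2 and not 11.2.3, and no rule says which prevails. Section 11.2.3 cannot act as tie-breaker while it disagrees with 11.2.2: tumor in another ipsilateral lobe 2-3 cm from the PTV is distant in one and local-regional in the other. Section 11.2.3 itself warns that recurrence rates can vary with the definition used.

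**Conclusion.** The wording is inconsistent within the definition of the primary endpoint. It is not an intended rule, and it has not been shown to affect results. The site list after SBRT differs between the opening definition, the SBRT paragraph and the closing paragraph of 11.2.2, and 11.2.3 differs again. The literal reading of the closing paragraph would work against SBRT, because its target-lesion rule fits only that arm.

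The fall from 0.91 to 0.72, 0.47 or 0.26 should not be read as an expected loss of power. It is an upper bound at each assumed rate. It requires every distant-only lesion to be misclassified, in one arm only, despite 11.2.3, and it rests on an assumed test form and on 0.20 as a one-sided level. Partial misclassification would cost less, and an assessor who reads 11.2.2 with 11.2.3 would probably score no brain or bone lesion as local. The 2-3 cm and same-lobe discrepancies remain even for that assessor.

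This is a clarification to make before events are scored. It leaves the sample size at 36 per arm, 76 in total.

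**What to change.** 1. In the closing paragraph of 11.2.2, state that a new lesion counts as local-regional progression only if it lies at a site listed above for local-regional failure, and that a new lesion elsewhere is distant failure.
2. Make the opening definition of 11.2.2 and section 13.1.1 refer to that single site list in place of their shorter description of primary tumor and nodal regions.
3. State that 11.2.2 governs the primary endpoint where it differs from 11.2.3, and that 11.2.3 serves the patterns-of-failure analysis.

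The cost is a few sentences of text. No extra scans, data items or patients are needed.

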11.2.3 Guidelines for Assessing Failure Patterns After SBRT and RODS

The definition of local failure is critical; recurrence rates may vary just due to varying definitions [259]. Participating physicians should be trained in the use of a standardized recording system. The distance between the center of recurrent tumor and the edge of the treated lesion will be measured as part of the following classification.

Type of Recurrence	Modality	Description (after treatment effects have subsided)
Local Failure		
Primary tumor failure (PLF)	SBRT	Appearance of residual tumor located within the extent of the primary targeted tumor.
Marginal failure (MF)	RODS/SBRT	RODS: Appearance of tumor \leq 2 cm in any direction of the staple-line or the structures immediately adjacent to prior tumor site (chest wall/ mediastinum/ diaphragm/ spine). SBRT: Appearance of tumor \leq 2 cm in any direction of the primary tumor PTV* or structures immediately adjacent to primary tumor (lung/ chest wall, mediastinum/ diaphragm/ spine).
Involved Lobe failure (ILF)	RODS/SBRT	RODS: Appearance of tumor $>$ 2 cm in any direction of the staple-line or the structures

		immediately adjacent to prior tumor site (chest wall/ mediastinum/ diaphragm/ spine). SBRT: Appearance of tumor > 2 cm in any direction of the primary tumor or structures immediately adjacent to primary tumor (lung/ chest wall, mediastinum/ diaphragm/ spine).
Port site/wound failure (PWF)	RODS	Appearance of tumor at a port or incision site after VATS or open resection.
Regional Nodal Failure		
Hilar nodal failure (HNF)	RODS/SBRT	Appearance of tumor in ipsilateral hilar nodal regions
Ipsilateral mediastinal nodal failure (MNF)	RODS/SBRT	Appearance of tumor in ipsilateral mediastinal and/or subcarinal nodal regions .
Contra-lateral mediastinal nodal failure (CNF)	RODS/SBRT	Appearance of tumor in contralateral mediastinal nodal regions .
Contralateral hilar nodal failure (CNF)	RODS/SBRT	Appearance of tumor in contralateral hilar nodal regions
Supraclavicular nodal failure (SNF)*	RODS/SBRT	Appearance of tumor in ipsilateral and contralateral supraclavicular nodal regions
Distant Failure		
Non-primary lobe failure (NLF)##	RODS/SBRT	Appearance of tumor within another ipsilateral (non-primary) lobe, ≥ 2 cm from the original planning target volume
Distant metastatic failure (DMF)	RODS/SBRT	Appearance of tumor deposits characteristic of NSCLC metastasis (chest wall other than incision sites, mediastinal structures/diaphragm, malignant pleural/pericardial effusion), contralateral lung and/or other distant sites.

*This is classified as distant nodal failure in RTOG 1021/ACOSOG Z4099.

#This is classified as local-regional failure in RTOG 1021/ACOSOG Z4099.

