11.1.1 Details of Follow-Up Evaluations

11.1.1.1 In follow up, PET and CT scans are required to document disease relapse/progression. Biopsy of the relapse/progression site is encouraged, but not required. Submission of the biopsy report (if applicable) and scan reports is required (see Schedule of Forms). Submission of imaging studies (scans with recurrent disease and the scans used for reference) is required for patients with recurrent disease.

Chest CT with IV contrast will be performed at least at 3, 6, 9, 12, 18, 24, and 36 months after completion of treatment (the date of surgery or at the last day of SBRT) per current standard of care. Response evaluation after SBRT can sometimes be difficult as fibrosis and subclinical radiographic changes are observed in a majority of patients. A solid pattern of fibrosis often may be misinterpreted as recurrent disease [267]. Regular radiological follow-up is required to establish local control. 18F-FDG PET can be helpful in distinguishing fibrosis from tumor recurrence, but treated volumes can show 18F-FDG uptake related to therapy for at least 12 months after treatment [162]. Careful radiological follow-up of patients is paramount in patients treated by RODS, as salvage surgery or definitive chemoradiotherapy might still be possible in case of local or regional recurrence [268-269].

11.1.1.2 In follow up, pulmonary function tests should be done per the treating physician's discretion.

11.1.1.3 After treatment is completed, patients will be seen in follow up every 3 months for years 1-2 years, every 6 months for year 3, then annually until publication of study results.

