11.2 Measurement of Response

11.2.1 Guidelines for Assessing Treatment Response after SBRT

11.2.1.1 CT Tumor Response

Tumor response on CT will be assessed per RECIST 1.1, as described below; see http://ctep.cancer.gov/protocolDevelopment/docs/recist_guideline.pdf for additional details.

- Complete Response (CR): Disappearance of all target lesions. Any pathologic lymph nodes (whether target or non-target) must have reduction in short axis to <10 mm)
- Partial Response (PR): At least a 30% decrease in the sum of diameters of target lesions, taking as reference the baseline sum diameters.
- Progressive Disease (PD): At least a 20% increase in the sum of diameters of target lesions, taking as reference the *smallest sum on study* (this includes the baseline sum if that is the smallest on study). In addition to the relative increase of 20%, the sum must also demonstrate an absolute increase of at least 5 mm. (*Note:* the appearance of one or more new lesions is also considered progression).
- Stable Disease (SD): Neither sufficient shrinkage to qualify for PR nor sufficient increase to qualify for PD, taking as reference the smallest sum diameters while on study.

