13.2 Secondary Endpoints

13.2.1 Overall survival;

13.2.2 Disease-free survival;

13.2.3 Frequency of site-specific failure (patterns of failure);

13.2.4 Time to local-regional tumor failure and distant metastases;

13.2.5 PET tumor response;

13.2.6 Frequency of adverse events, graded by CTCAE, v. 4;

13.2.7 Trial feasibility parameters.

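### The SBRT primary-tumor-failure code in Section 11.2.3 has no growth criterion and conflicts with Section 11.2.2, so residual tumor that has not progressed can be coded as local failure in the secondary patterns-of-failure comparison

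*Combined protocol and SAP*

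**What the plan says.** Two sections of the protocol describe local failure after SBRT.

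- **Section 11.2.2** holds the rule that Section 13.1.1 cites for the primary endpoint. It states: "Local regional progression after SBRT includes tumor progression on CT per RECIST criteria, confirmed by PET/CT, within the same lobe", and goes on to nodal regions and a 3 cm zone around the PTV. The threshold follows: "Local progression is defined as at least a 20% increase in the sum of diameters of the target lesions", counted from the smallest sum on study, with an absolute rise of at least 5 mm as well. A new lesion also counts.
- **Section 11.2.3** holds a table of failure types. Its lead-in says: "The distance between the center of recurrent tumor and the edge of the treated lesion will be measured as part of the following classification". The description column is headed "Description (after treatment effects have subsided)". The first row under local failure, PLF, is for SBRT only and reads "Appearance of residual tumor located within the extent of the primary targeted tumor".

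Three other places bear on the point. Section 11.2.1.1 recognises stable disease as an outcome: "Neither sufficient shrinkage to qualify for PR nor sufficient increase to qualify for PD". Section 11.1.1.1 warns that after SBRT "fibrosis and subclinical radiographic changes are observed in a majority of patients", and it requires both PET and CT to document relapse. Section 13.2.3 lists as a secondary endpoint "Frequency of site-specific failure (patterns of failure)". Section 13.5.2 plans contingency tables and logistic regression for site-specific failure proportions and points to Section 11.2.3 for failure patterns. Section 2.2.3 makes the between-arm comparison of those patterns an objective.

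**The concern.** SBRT leaves the primary tumor in place, so a tumor that shrinks or stays the same size is a normal form of local control. The PLF row turns on the presence of residual tumor, not on its growth. A coder who follows the row as written can record a local failure in a patient whom Section 11.2.2 counts as controlled.

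At stake is a planned secondary comparison between arms. The same patient could be a success in the primary analysis and a local failure in the patterns-of-failure table. Surgery removes the primary, so no RODS patient can be miscoded in this way, and any error raises the SBRT count alone. Section 11.2.3 itself warns that recurrence rates can shift merely because definitions differ, and it asks for physicians to be trained in this recording system.

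**Working it through.** **1. The two rules side by side (SBRT, within the primary target)**

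| Element | Section 11.2.2 | Section 11.2.3, PLF row |
|---|---|---|
| Trigger | RECIST progression on CT | Residual tumor |
| Relative growth | At least 20% over the smallest sum | None stated |
| Absolute growth | At least 5 mm | None stated |
| PET/CT confirmation | Stated in the rule | Not in the row; Section 11.1.1.1 requires PET and CT to document relapse |
| Timing | None | After treatment effects subside; no time point |

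**2. Applying both rules to three hypothetical patients**

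Assume that what remains at 24 months is tumor and not fibrosis.

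| Patient | Change | Section 11.2.2 | PLF wording |
|---|---|---|---|
| A: 24 mm, now 12 mm (smallest) | (24 − 12)/24 = 50% decrease: partial response | Controlled | Met |
| B: 20 mm, now 18 mm (smallest) | (20 − 18)/20 = 10% decrease: stable disease | Controlled | Met |
| C: 24 mm, smallest 12 mm, now 19 mm | (19 − 12)/12 = 58% and 7 mm increase: progression | Failure, if PET/CT confirms | Met |

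The sections agree on C and disagree on A and B.

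**3. Is the table only a site label for events already established under Section 11.2.2?**

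If it were, the missing threshold would do no harm. Two features count against this. The table separates marginal from involved-lobe failure at 2 cm, where Section 11.2.2 uses 3 cm. It also lists sites that Section 11.2.2 does not: port or incision site, contralateral supraclavicular nodes, another ipsilateral lobe and distant sites. No sentence says that Section 11.2.2 must be met before PLF is assigned.

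**4. What can be said about size**

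The plan figure used here is 36 evaluable patients per arm (Section 13.3). It reproduces with 90% against 75%, power 0.80 and an error rate of 0.20 taken as one-sided (Section 13.3 does not state the sidedness): n = 0.8416² × [√(2 × 0.825 × 0.175) + √(0.9 × 0.1 + 0.75 × 0.25)]² / 0.15² = 35.6, rounded up to 36. The coding issue does not alter this figure.

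Each controlled SBRT patient coded PLF adds 1/36 = 2.8 percentage points. If a share r of controlled patients keeps residual tumor without progression, and all of them are coded literally, the added codes are 36 × c × r, where c is true SBRT local-regional control. The documents give no r, so the values below are assumptions.

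| r (assumed) | c = 0.75 (27 controlled) | c = 0.90 (32.4 controlled) |
|---|---|---|
| 5% | 1.35 (3.75 points) | 1.62 (4.5 points) |
| 20% | 5.4 (15 points) | 6.5 (18 points) |
| 40% | 10.8 (30 points) | 13.0 (36 points) |
| 60% | 16.2 (45 points) | 19.4 (54 points) |

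These figures show what literal coding would do at each assumed share. They are not estimates. The matching figure for RODS is zero by construction.

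**The case against.** The strongest reply is that the table sorts recurrences by place. Its first column is headed as a type of recurrence, its lead-in measures from recurrent tumor, and none of its rows carries a growth threshold. On that view, PLF simply means a recurrence located in the treated primary. The row also speaks of tumor appearing, which fits a mass that merely persists poorly. The column header screens out treatment effects. Section 11.1.1.1 requires PET as well as CT to document relapse. Section 6.7.2 treats it as an error to call a stable or shrinking tumor progressive disease. A persistent CT mass need not be tumor at all. The lack of a RODS counterpart is inherent in surgery, and the table has a RODS-only code of its own for port or wound failure.

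Most of this stands as evidence of intent, and it makes the literal reading possible rather than certain. It does not remove the conflict. PLF is the only row that speaks of residual tumor, and residual tumor is not recurrent tumor. The header excludes fibrosis and inflammation but not a stable viable remnant, and it gives no time point. Sections 11.2.1.1 and 11.2.1.2 both have partial-response and stable categories, so the plan accepts that a treated tumor can remain without progressing. The PET and CT requirement governs how relapse is documented; it does not say that residual tumor must have grown.

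A reader might infer that the plan orders all stable or shrinking SBRT tumors to be counted as failures. The documents do not support that: it is one literal reading of one cell, set against a recurrence framing.

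**Conclusion.** The PLF row conflicts with Section 11.2.2. Followed literally, it allows SBRT patients with stable or shrinking residual tumor to be coded as local failures in the secondary patterns-of-failure comparison although they are controlled under the primary endpoint. Any such error runs against SBRT only. Its size cannot be stated, because it depends on how many patients keep a non-progressing tumor and on how coders read the row, and the documents give neither.

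Three stronger inferences should be resisted.

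- **That the primary endpoint is biased or loses power.** Section 13.1.1 cites Section 11.2.2, so the primary analysis as written is unaffected.
- **That time to local-regional failure is distorted.** No such analysis is specified to use the Section 11.2.3 codes, and Section 13.5.1 places that analysis under the primary-endpoint methods.
- **That SBRT local failure would appear as 40% to 70%.** Those totals come from adding the 5.4 to 16.2 codes (r from 20% to 60%, c = 0.75) to the 9 failures expected at 75% control, giving 14.4 to 25.2 of 36. The shares are assumed. The 9 are local-regional events, and Section 13.3 attributes the expected SBRT deficit mainly to the absence of nodal dissection, so the sum is not a local failure rate.

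**What to change.** Reconcile the two sections in three steps.

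1. Replace the PLF description with wording such as: *Progression of the treated primary that meets Section 11.2.2, including its PET/CT confirmation, and lies inside the original target. Residual tumor that has not progressed is not a failure.*
2. Add a sentence to Section 11.2.3 that an SBRT PLF code is assigned only to an event that already meets Section 11.2.2.
3. Limit that sentence to PLF. Distant failures and other codes that fall outside Section 11.2.2 must not be made to depend on it.

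The cost is one table cell and one sentence, with no new scans, readers or patients. PLF codes already assigned can be checked against the recurrence scans and reference scans that Section 11.1.1.1 requires sites to submit.

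### In the Section 11.2.3 failure table the Local and Distant classes overlap, and the row meant to separate other-lobe recurrences cannot be applied after surgery

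*Combined protocol and SAP*

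**What the plan says.** The Section 11.2.3 table places marginal failure (MF) and involved-lobe failure (ILF) under Local, and non-primary-lobe failure (NLF) and distant metastatic failure (DMF) under Distant. All four rows are labelled for both arms.

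- **ILF after RODS:** "RODS: Appearance of tumor $>$ 2 cm in any direction of the staple-line or the structures" that are "immediately adjacent to prior tumor site (chest wall/ mediastinum/ diaphragm/ spine").
- **ILF after SBRT:** "SBRT: Appearance of tumor > 2 cm in any direction of the primary tumor or structures immediately adjacent to primary tumor".
- **NLF, both arms:** "Appearance of tumor within another ipsilateral (non-primary) lobe, ≥ 2 cm from the original planning target volume".
- **DMF, both arms:** "Appearance of tumor deposits characteristic of NSCLC metastasis (chest wall other than incision sites, mediastinal structures/diaphragm, malignant pleural/pericardial effusion"), plus contralateral lung and other distant sites.
- **Measuring rule, in the text above the table:** "The distance between the center of recurrent tumor and the edge of the treated lesion will be measured as part of the following classification".
- **Nodal codes:** contralateral mediastinal failure is coded CNF, and the next row is "Contralateral hilar nodal failure (CNF"), the same code.

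Section 8.1.1 makes the Arm 1 operation a lobectomy, bilobectomy or pneumonectomy. Sections 13.2.3 and 13.2.4 make site-specific failure, and time to local-regional failure and to distant metastases, secondary endpoints; objective 2.2.3 compares them between arms. Section 13.5.2 plans contingency tables, logistic regression and competing-risks methods for them and refers to Section 11.2.3. Local-regional control, the primary endpoint, is defined separately in Section 11.2.2, with a radius of 3 cm from the staple line or the PTV.

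**The concern.** A pattern-of-failure tabulation, and a competing-risks analysis of distant metastases, need each failure assigned to one class by a rule that two coders would apply alike. Here some lesions satisfy a Local and a Distant row together, and nothing says which row wins. Section 11.2.3 itself acknowledges that the definition chosen can change a recurrence rate.

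The problem is not symmetric. The distance test in the NLF row can be carried out in an SBRT patient and not in a RODS patient. If coders fall back on the ILF wording after surgery, the same biological event may be counted as Local in one arm and Distant in the other. That could create or hide a between-arm difference in distant failure.

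**Working it through.** **1. Lesions set against the rows.**

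| Lesion | Local row met | Distant row met | What decides |
|---|---|---|---|
| RODS, remaining ipsilateral lobe, more than 2 cm from staple line | ILF, by its description | NLF by site; distance not testable (no PTV) | Nothing |
| RODS, non-incision chest wall, diaphragm or mediastinal structure near the tumor site | MF or ILF, by distance | DMF | Nothing |
| SBRT, same structures | MF or ILF, by distance | DMF | Nothing |
| SBRT, other ipsilateral lobe, more than 2 cm from PTV | ILF only if the row's name is ignored | NLF, testable | The ILF row name |
| SBRT, other ipsilateral lobe, exactly 2 cm from PTV | MF | NLF | Nothing (boundary case only) |

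The first row is the arm-specific defect. The second and third are common to both arms.

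**2. Relation to Section 11.2.2.** A lesion in another ipsilateral lobe 2 to 3 cm from the PTV is local-regional under 11.2.2 (within 3 cm) and Distant under NLF (at least 2 cm). Giving RODS a 2 cm NLF cut-off from the staple line would copy that clash into the surgical arm, so a repair has to address it.

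**3. Overlaps that stay inside one class.** After SBRT, MF reaches 2 cm from the PTV, while ILF starts beyond 2 cm from the tumor. The bands overlap by the margin between tumor and PTV. With the direct expansion in Section 6.1.5 (0.5 cm axial, 1.0 cm craniocaudal), lesions 2.0 to 2.5 cm away axially, or 2.0 to 3.0 cm craniocaudally, are both MF and ILF. Section 6.1.5 also allows an ITV plus set-up uncertainty (for example 4 to 5 mm), so the width depends on the method used. MF and ILF are both Local, and both CNF rows are Regional Nodal.

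**4. Weight of one recoded patient.** The plan gives no figure for misclassification, so only the denominators can be checked. For 90% versus 75%, one-sided error 0.20 and power 0.80, with pooled proportion 0.825 and z = 0.8416:

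n = [0.8416 × (√(2 × 0.825 × 0.175) + √(0.90 × 0.10 + 0.75 × 0.25))]² / 0.15² = [0.8416 × (0.5374 + 0.5268)]² / 0.0225 = 35.6, rounded up to 36 per arm.

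This reproduces the 36 per arm in Section 13.3. Then 72 × 1.05 = 75.6, rounded up to 76, or 38 per arm.

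- One patient: 1/38 = 2.6 points; 1/36 = 2.8 points, with local and distant moving in opposite directions.
- Assumed range of 1 to 3 recoded patients in an arm (the documents give no number): 2.6 to 7.9 points with 38, 2.8 to 8.3 points with 36.
- For scale, at the assumed 90% control, 0.10 × 36 = 3.6 RODS local-regional failures are expected by 2 years.

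**The case against.** The strongest reply is that the row names should be read with the descriptions. Taken literally, the SBRT wording of ILF has no lobe limit either, and the RODS wording would reach even the contralateral lung, which no coder would call an involved lobe. If the name confines ILF in both arms, a recurrence in a remaining lobe after surgery is NLF, hence Distant, and that row is labelled for RODS. A table footnote notes a category classed as local-regional in another trial; if it belongs to NLF, the Distant placement was deliberate.

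Much of this stands: a reader should not infer that the table directs coders to call RODS other-lobe recurrences Local, or that ILF is unbounded in one arm only. It does not remove the defect. If the name governs, the RODS entry for ILF is essentially empty after lobectomy, yet the table writes one out. NLF still has a distance criterion that cannot be evaluated in a RODS patient. Neither reading makes the table work as written.

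For chest wall, mediastinal and diaphragm lesions, it can be said that the Local rows concern structures next to the tumor site and DMF concerns deposits typical of metastasis. That narrows the overlap, but a deposit on an adjacent structure can still meet both, in either arm.

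The remaining safeguards are training of physicians (11.2.3) and submission of scans and reports at recurrence (11.1.1.1, 12.2). They make recoding possible but do not say which class takes precedence.

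**Conclusion.** The table should be corrected before failure patterns are analyzed. The Local/Distant overlap and the missing surgical reference for NLF bear on 13.2.3 and on time to distant metastases in 13.2.4. Time to local-regional failure is also exposed if it is coded from this table rather than from 11.2.2. Each recoded patient shifts an arm's local and distant proportions by about 2.6 to 2.8 points. How many would be recoded is unknown, so this is a weight per case and not an estimate of bias.

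Four stronger inferences are not supported:

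- **That the primary endpoint is affected.** It rests on 11.2.2.
- **That a between-arm bias of known direction exists.** Arm-dependent coding is possible, but it depends on how coders read the ILF row.
- **That the MF/ILF bands or the shared CNF code disturb time to distant metastases.** They stay within Local and Regional Nodal respectively and blur only the finer pattern of failure.
- **That the text and table conflict on measuring from the center or the edge of a recurrence.** The text states a center rule, and the rows name neither, so the text governs.

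**What to change.** 1. Confine ILF to the treated lobe, measured from the PTV, and mark it not applicable when the whole lobe was resected. This also closes the MF/ILF overlap after SBRT.
2. Give NLF a staple-line reference for RODS patients.
3. Add one precedence rule, identical in both arms, for chest wall, mediastinal and diaphragm deposits.
4. State that a lesion counted as local-regional under 11.2.2, including one within 3 cm of the staple line or PTV, is not also counted as distant in 13.2.4.
5. Give contralateral mediastinal and contralateral hilar failure separate codes.
6. Keep the stated center-of-recurrence rule and apply it in both arms.

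The cost is rewording of the table and form, and recoding of recurrences already recorded from the submitted scans and reports. The rules should be fixed before failure sites are tabulated by arm.
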